9.3. Safety Evaluations/Outcomes

9.3.1. Bleeding Events

The primary safety outcome will be major bleeding events, as defined below. Clinically relevant non-major bleeding events and trivial (minimal) bleeding will be secondary safety outcomes.

Bleeding events will be adjudicated by CIAC using the ISTH recommendations.^{5,27} The following bleeding criteria are consistent across the rivaroxaban pediatric program:

Major bleeding is defined as overt bleeding and:

- Associated with a fall in hemoglobin of 2 g/dL or more; or
- Leading to a transfusion of the equivalent of 2 or more units of packed red blood cells or whole blood in adults ; or
- Occurring in a critical site: intracranial, intraspinal, intraocular, pericardial, intra-articular, intramuscular with compartment syndrome, retroperitoneal; or
- Contributing to death.

Clinically relevant non-major bleeding is defined as overt bleeding not meeting the criteria for major bleeding but associated with:

- Medical intervention, or
- Unscheduled contact (visit or telephone call) with a physician, or
- (Temporary) cessation of study treatment, or
- Discomfort for the subject such as pain, or
- Impairment of activities of daily life (such as loss of school days or hospitalization).

Trivial (minimal) bleeding is defined as any other overt bleeding event that does not meet criteria for clinically relevant non major bleeding.

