9.3.2. Approach to the Subject with a Bleeding Event

If a subject has a serious bleed during study treatment, the following routine measures could be considered by the treating physician:

- Consider usual treatment for bleeding, including blood transfusion, and/or fresh frozen plasma if needed
- Consider that other causes besides thromboprophylaxis medication can be contributory to the seriousness of the bleeding event (eg, thrombocytopenia, and other coagulopathies; kidney and liver dysfunction; concomitant medications), and treat accordingly
- Delay the next ASA or rivaroxaban administration or temporarily discontinue treatment, if indicated

- If the subject is treated with rivaroxaban, a blood sample for PK and PD testing should be obtained

NOTE: Partial reversal of prothrombin time prolongation has been seen after administration of prothrombin complex concentrates (PCCs) in healthy volunteers. The use of other procoagulant reversal agents like activated prothrombin complex concentrate (APCC) or recombinant factor VIIa (rFVIIa) has not been evaluated.

If severe bleeding cannot be controlled, however, consider administration of one of the following procoagulants (both according to the dosages advised in the package insert):

- 4 factor concentrate
- Recombinant factor VIIa (NovoSeven[®])

Protamine sulfate and vitamin K are not expected to affect the anticoagulant activity of rivaroxaban.

Any products administered to control bleeding should be entered in the CRF.

Parents/ legally acceptable representatives should call the study physician, if the subject has signs and symptoms of clinically significant bleeding, for example:

- bleeding (eg, nose or gum bleeding) that does not stop within 10 minutes
- coughing or throwing up blood
- dark-colored urine or black stools
- red or black-and-blue marks on the skin that get larger

If the subject has a bleeding incident, the parent/ legally acceptable representatives should consult the study physician in addition to their own cardiologist (if different) and always inform him/her of the date/time the subject took the last dose of anticoagulant medication. For severe bleeding, subjects should be moved to the nearest emergency room.

After resolution of the bleeding event, restarting study drug may be considered based on the clinical judgment of the investigator.

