## 4.1 Bleeding Events

The primary safety outcome is the major bleeding events, as defined below. Clinically relevant non-major bleeding events and trivial (minimal) bleeding will be secondary safety outcomes.

Bleeding events will be adjudicated by the CIAC using the International Society on Thrombosis and Hemostasis (ISTH) recommendations (Buller 2007, Schulman 2005).

Major bleeding is defined as overt bleeding and:

- Associated with a fall in hemoglobin of 2 g/dL or more; or
- Leading to a transfusion of the equivalent of 2 or more units of packed red blood cells or whole blood in adults; or
- Occurring in a critical site: intracranial, intraspinal, intraocular, pericardial, intra-articular, intramuscular with compartment syndrome, retroperitoneal; or
- Contributing to death.

Clinically relevant non-major bleeding is defined as overt bleeding not meeting the criteria for major bleeding but associated with:

- Medical intervention, or
- Unscheduled contact (visit or telephone call) with a physician, or
- (Temporary) cessation of study treatment, or
- Discomfort for the subject such as pain, or
- Impairment of activities of daily life (such as loss of school days or hospitalization).

Trivial (minimal) bleeding is defined as any other overt bleeding event that does not meet criteria for clinically relevant non major bleeding.

The main description will be based on Safety Analysis Set during the On-treatment period (bleeding events confirmed by the CIAC).

Incidence rates (number of subjects with bleeding event during the period divided by the number of subjects at risk at the beginning of the period) and the respective 95% CIs will be calculated for the major and clinically relevant non major bleedings by treatment group. Cumulative

incidence rates (time to first event; Kaplan-Meier) will be calculated for the major bleeding and clinically relevant non-major bleeding.

In addition, listing for all bleedings will be provided, including those that are reported more than 2 days after stop of study medication.

Baseline demographics and disease characteristics relationship to bleeding risk may be explored.

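### An unscheduled call or visit is enough to make a bleed clinically relevant, so this secondary outcome can follow families' contact behaviour, and SAP 4.1 omits the broader by-arm bleeding analysis planned in Protocol 11.4

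*Protocol*

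**What the plan says.** **Definition.** Protocol 9.3.1, repeated in SAP 4.1, lists five criteria for clinically relevant non-major (CRNM) bleeding, joined by "or" in sense: any one suffices. One of them is "Unscheduled contact (visit or telephone call) with a physician". Trivial bleeding is what remains: "Trivial (minimal) bleeding is defined as any other overt bleeding event that does not meet criteria for clinically relevant non major bleeding". On status, the protocol states: "Clinically relevant non-major bleeding events and trivial (minimal) bleeding will be secondary safety outcomes".

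**Instructions to families.** Protocol 9.3.2 has two adjacent instructions. The first reads "Parents/ legally acceptable representatives should call the study physician, if the subject has signs and symptoms of clinically significant bleeding" and gives examples, such as bleeding that has not stopped within 10 minutes. The second reads "If the subject has a bleeding incident, the parent/ legally acceptable representatives should consult the study physician" and sets no severity limit.

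**Blinding.** Treatment is open-label (Protocol 5). The adjudication committee works blinded to treatment (Protocol 9.7.4).

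**Analysis.** In SAP 4.1, incidence rates and 95% CIs "will be calculated for the major and clinically relevant non major bleedings by treatment group", and Kaplan-Meier cumulative incidences "will be calculated for the major bleeding and clinically relevant non-major bleeding". The only output in that section that reaches trivial bleeding is a listing of all bleeds. Protocol 11.4 is broader. It plans a by-arm summary of on-treatment bleeding events and by-arm Kaplan-Meier incidence for time to first bleeding event, neither restricted by category.

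**The concern.** Because contact alone meets the definition, each call or visit about an otherwise trivial bleed moves that bleed into the CRNM category. A family's decision to call may depend on knowing that the child takes a new anticoagulant rather than ASA. Protocol 3.2 itself says that rivaroxaban carries an increased risk of bleeding. Blinded adjudication cannot correct for this, since whether a contact took place is already a fact in the file when the committee receives it.

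Comparing safety with ASA is part of the primary objective of Part B, with about 90 children at 2:1, or about 60 versus 30. Major bleeds may be few. With none observed, the exact two-sided 95% upper limits would be 1 − 0.025^(1/60) = 6.0% and 1 − 0.025^(1/30) = 11.6%. Readers would then lean on CRNM bleeding, and a difference there could partly describe contacts rather than bleeding. SAP 4.1 names no by-arm total that is unaffected by this shift.

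**Working it through.** The plan states no bleeding rate, contact rate or power, so there is no figure of its own to reproduce. The allocation is 90 × 2/3 = 60 and 90 × 1/3 = 30. What follows is an illustration, and every rate in it is an assumption.

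**Inputs (assumed)**
- p: share of children with a non-major overt bleed, equal in both arms, 20% to 40%.
- s: share of those who meet another CRNM criterion, 0 or 25%.
- c: probability of an unscheduled call or visit for the rest, allowed to differ by arm.
- One bleed per child; major bleeds are left aside.

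**Formulas**
- Observed CRNM risk = p × [s + (1 − s) × c]
- Trivial risk = p − CRNM risk

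**Worked case, p = 30%, s = 25%**
- No contact criterion: 0.30 × 0.25 = 7.5%
- c = 50%: 0.30 × (0.25 + 0.75 × 0.50) = 18.75%
- c = 80%: 0.30 × (0.25 + 0.75 × 0.80) = 25.5%
- c = 100%: 30%, and the trivial category is empty

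| Contact, rivaroxaban / ASA | CRNM, rivaroxaban | CRNM, ASA | Ratio | Trivial, rivaroxaban | Trivial, ASA |
|---|---|---|---|---|---|
| 50% / 50% | 18.75% | 18.75% | 1.00 | 11.25% | 11.25% |
| 60% / 50% | 21.0% | 18.75% | 1.12 | 9.0% | 11.25% |
| 80% / 50% | 25.5% | 18.75% | 1.36 | 4.5% | 11.25% |
| 90% / 30% | 27.75% | 14.25% | 1.95 | 2.25% | 15.75% |
| 100% / 100% | 30.0% | 30.0% | 1.00 | 0% | 0% |

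**Range.** The ratio does not depend on p. With s = 0 it is simply the ratio of the contact probabilities: 1.20, 1.60 and 3.00 for the three unequal rows. For 80% versus 50%, the gap runs from 4.5 points (p = 20%, s = 25%) to 12 points (p = 40%, s = 0).

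**Reading.** Equal contact raises the level of CRNM bleeding but creates no gap. Unequal contact creates a gap although bleeding is the same. In every row CRNM plus trivial is 30% in both arms, so the total is not affected by the shift. Its precision would be modest: 18/60 has an exact 95% CI of 18.8% to 43.2%, and 9/30 has 14.7% to 49.4%.

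**SAP against protocol**

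| Outcome | Protocol 11.4 | SAP 4.1 |
|---|---|---|
| Major, CRNM | Within the by-arm summary; listings | By-arm incidence, CI, Kaplan-Meier; listing |
| Trivial | Within the by-arm summary | Listing only |
| Any bleeding | By-arm summary; Kaplan-Meier for time to first event | Listing only |

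**The case against.** A reader might infer that parents are told to call about every bleed. The documents do not settle that. The first instruction in Protocol 9.3.2 is limited to clinically significant bleeding, and the second can be read as saying mainly whom to consult and what to report. The two sentences set different thresholds; that ambiguity is what can be shown.

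A reader might also infer that the arms are bound to differ. Both arms receive the same instructions, and full compliance would enlarge the category equally. A false gap needs contact behaviour that differs by arm, and no figure in the documents shows that it does.

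Nor is it right that the plan has no by-arm total at all. Protocol 11.4 provides one. Bleeds are also recorded as adverse events (Protocol 12.3.1) and counted by arm in those tables, though by preferred term and not by adjudicated category. SAP 2 promises by-arm counts and percentages in general terms, and the table shells are in a separate document not available here. The gap is therefore that SAP 4.1 is narrower than the protocol.

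Finally, a total of any overt bleeding does not remove differential noticing or reporting: more alert families may report more trivial bleeds. Outcome assessments at the same scheduled contacts in both arms limit this, but the later visits are months apart. This objection stands.

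**Conclusion.** The point holds in a limited form. Contact alone is sufficient for CRNM bleeding, blinded adjudication cannot reverse it, and SAP 4.1 leaves out by-arm incidence for trivial and for any overt bleeding. The category can be inflated, and it can differ falsely between arms if contact differs. Whether it does, and by how much, cannot be learned from the documents. The ratios of 1.12 to 3.00 for unequal contact rest entirely on assumed rates, and the ratio is 1.00 when contact is equal.

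The consequence is confined to a descriptive secondary safety outcome. Major bleeding does not use the contact criterion and no hypothesis is tested, so nothing here weakens the primary safety outcome. The change is worth making because it is cheap and brings the SAP back to the scope of the protocol.

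**What to change.** 1. Keep the bleeding definition, which Protocol 9.3.1 says is consistent across the pediatric programme.
2. In SAP 4.1, add by-arm incidence with 95% CI and Kaplan-Meier for any overt bleeding and for trivial bleeding, on the same analysis set and period as the existing bleeding outputs. Trivial bleeding should be read beside CRNM bleeding, because reclassification moves the two in opposite directions.
3. Where the adjudication data hold the qualifying criterion, show CRNM bleeding with and without events that qualify by unscheduled contact alone.
4. Reconcile the two contact instructions in Protocol 9.3.2 so that sites and families work from one threshold. Which threshold is right is a clinical matter for the sponsor.
5. State in the report that any overt bleeding is protected against reclassification but not against differential reporting.

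The cost is one or two more tables, one retained data field and a wording clarification. Item 3 depends on what the adjudication record captures. That is governed by the committee's charter, which is not among the documents.

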9.3.2. Approach to the Subject with a Bleeding Event

If a subject has a serious bleed during study treatment, the following routine measures could be considered by the treating physician:

- Consider usual treatment for bleeding, including blood transfusion, and/or fresh frozen plasma if needed
- Consider that other causes besides thromboprophylaxis medication can be contributory to the seriousness of the bleeding event (eg, thrombocytopenia, and other coagulopathies; kidney and liver dysfunction; concomitant medications), and treat accordingly
- Delay the next ASA or rivaroxaban administration or temporarily discontinue treatment, if indicated

- If the subject is treated with rivaroxaban, a blood sample for PK and PD testing should be obtained

NOTE: Partial reversal of prothrombin time prolongation has been seen after administration of prothrombin complex concentrates (PCCs) in healthy volunteers. The use of other procoagulant reversal agents like activated prothrombin complex concentrate (APCC) or recombinant factor VIIa (rFVIIa) has not been evaluated.

If severe bleeding cannot be controlled, however, consider administration of one of the following procoagulants (both according to the dosages advised in the package insert):

- 4 factor concentrate
- Recombinant factor VIIa (NovoSeven[®])

Protamine sulfate and vitamin K are not expected to affect the anticoagulant activity of rivaroxaban.

Any products administered to control bleeding should be entered in the CRF.

Parents/ legally acceptable representatives should call the study physician, if the subject has signs and symptoms of clinically significant bleeding, for example:

- bleeding (eg, nose or gum bleeding) that does not stop within 10 minutes
- coughing or throwing up blood
- dark-colored urine or black stools
- red or black-and-blue marks on the skin that get larger

If the subject has a bleeding incident, the parent/ legally acceptable representatives should consult the study physician in addition to their own cardiologist (if different) and always inform him/her of the date/time the subject took the last dose of anticoagulant medication. For severe bleeding, subjects should be moved to the nearest emergency room.

After resolution of the bleeding event, restarting study drug may be considered based on the clinical judgment of the investigator.

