- k) If a suspected outcome event (thrombotic or bleeding event) occurs, the adjudication package is to be completed.
- l) Only vital status and thrombotic events (no bleeding events) will be assessed and an adjudication package will be completed.
- m) Adverse event assessment includes a review of all ongoing and new adverse events since the last visit for all visits through Month 12.
- n) A physical examination will be symptom-driven.
- o) Transthoracic echocardiograms will be obtained at screening, Month 6, and Month 12, or ESMD and whenever medically necessary, and results sent to the core laboratory. For screening see footnote 'a'.
- p) Hematology (complete blood count [CBC] with differential, platelet count); blood chemistry (liver function tests [alanine aminotransferase, ALT; aspartate aminotransferase, AST; total and direct bilirubin; alkaline phosphatase] and creatinine).
- q) Hematology and serum chemistry testing are done at screening (testing should be done after the Fontan procedure and results should be available within 21 days prior to Day 1, at Month 12 and ESMD visit). At Month 3 only serum chemistry laboratory tests are done. Prothrombin time and aPTT tests (should be done at screening visit only). Note: Hospital laboratory, local laboratory results, or central laboratory results are acceptable at screening, and the most recent clinical laboratory results will be used for screening if there are multiple laboratory results.
- r) Pharmacokinetics and (PT and aPTT) samples will be collected at all timepoints for central testing. If a subject experiences a major bleeding event while being treated with rivaroxaban, obtain PK and PD samples (see also Section 9.3.2 for approach to the subject with a bleeding event and Section 9.5 for sample instructions).
- s) Anti- factor Xa [FXa] assay samples will be collected only at these specific time points.
- t) To be collected at any timepoint during the visit (PK, PT, aPTT, hematology and chemistry testing). Parent/legally acceptable representative should document timing of the administered AM study drug dose.
- u) Allow at least 30 minutes from the previous sample.

TIME & EVENTS SCHEDULE – SUBJECTS PARTICIPATING IN PART B

| | Screening Period ^a | Open-Label Treatment Period ^c | | | | | | Follow-Up Contact ^d | ESMD Month 12 Follow-Up ^e |

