10.2.2. Permanent Discontinuation of Study Drug

A subject's study treatment should be discontinued permanently if:

- The investigator believes that for safety reasons (eg, adverse event or persistent noncompliance) it is in the best interest of the subject to discontinue study treatment
- The subject has a thrombotic event
- The subject develops any condition that requires treatment with anticoagulant or antiplatelet therapy
- The subject has a major bleeding event, eg, intracranial bleeding (for definitions of major bleeding see Section 9.3.1, Bleeding Events)
- The subject, his or her parents/legally acceptable representatives request to discontinue the study drug permanently

For subjects in Part A and Part B who prematurely and permanently discontinue the study drug for any reason, the ESMD visit will be performed as soon as possible after discontinuation of the study drug. A Follow-Up phone contact will be performed 30 days following the last dose of the study drug. In addition, an ESMD Month 12 Follow-Up phone contact will be conducted at the end of the planned treatment period. This excludes subjects who are enrolled after local reading of the Screening transthoracic echocardiogram rules out thrombosis, and subsequently reported to have thrombosis after central reading by the core laboratory of the same transthoracic echocardiogram. These subjects will be withdrawn from the study when the result of the echocardiogram by the core laboratory becomes available. Subjects will be asked to return for

the ESMD visit as soon as possible. They will not be required to have a repeat transthoracic echocardiogram as part of the ESMD. Subjects will go on to receive proper care according to the healthcare provider's judgment. They will be contacted by phone approximately 30 days (+/- 7 days) after last dose of study drug (Follow-Up Contact). An ESMD Month 12 follow up visit will not be required.

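### Protocol 9.3.2 allows study drug to be restarted after a bleed with no exception for major bleeding, while 10.2.2 says it should then be stopped permanently, and the protocol does not say which section governs

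*Protocol*

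**What the plan says.** **Protocol 9.3.2** opens with "If a subject has a serious bleed during study treatment, the following routine measures could be considered by the treating physician". Its measures include "Consider usual treatment for bleeding, including blood transfusion, and/or fresh frozen plasma if needed" and, on dosing, "Delay the next ASA or rivaroxaban administration or temporarily discontinue treatment, if indicated". It then covers the worst case: "If severe bleeding cannot be controlled, however, consider administration of one of the following procoagulants". Its last sentence is "After resolution of the bleeding event, restarting study drug may be considered based on the clinical judgment of the investigator". Permanent discontinuation is not mentioned, and 10.2.2 is not cited.

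**Time and Events Schedule**, footnote r for Part A and footnote s for Part B, both state: "If a subject experiences a major bleeding event while being treated with rivaroxaban, obtain PK and PD samples (see also Section 9.3.2 for approach".

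**Protocol 10.2.2** lists the circumstances in which treatment *should* be stopped for good. One is "The subject has a major bleeding event, eg, intracranial bleeding (for definitions of major bleeding see Section 9.3.1, Bleeding Events".

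**Protocol 10.2.1** allows a temporary stop for, among other things, a significant bleeding event. It lets drug be resumed whenever the investigator judges it safe.

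**SAP 2.2** removes from the Per-protocol Set a child whose drug was not permanently stopped when the protocol required it. **SAP 3.6** names the same failure as a category of major protocol deviation.

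**The concern.** Major bleeding is the primary safety outcome, and 10.2.2 gives a stopping rule for it. The section a site would open while managing the bleed gives a different message: hold or delay, then consider restarting. Three things could follow.

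- **Safety.** A child could go back on an anticoagulant or ASA after the event that the stopping rule is there for. Intracranial bleeding is the example in 10.2.2, and a history of it bars enrollment under exclusion criterion 4.
- **Uneven conduct.** Permanent discontinuation triggers an Early Study Medication Discontinuation visit with an echocardiogram and, later, a Month 12 contact. A restart does not. Two sites with the same event could take different paths.
- **Deviations.** A site could act on 9.3.2 and still be recorded as having failed to discontinue permanently.

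**Working it through.** This is a comparison of instructions, so the main check is textual. The plan gives no figure to reproduce.

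**1. Does 9.3.2 reach major bleeds?**
- The footnotes say so most directly. They name a major bleeding event and refer to 9.3.2 for the approach to the child. They are sampling instructions and concern rivaroxaban only, but 9.3.2 itself names both drugs.
- The section covers serious bleeding and severe bleeding that cannot be controlled.
- Transfusion is weaker evidence. It makes a bleed major only at the 9.3.1 threshold, "Leading to a transfusion of the equivalent of 2 or more units of packed red blood cells or whole blood in adults". Below that, with no other major criterion, a transfused bleed is a medical intervention and so clinically relevant non-major.

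The section therefore covers major bleeds, and others as well.

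**2. What does each section say about study drug after a major bleed?**

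| Section | Term used | Action on study drug | Exception or cross-reference |
|---|---|---|---|
| 9.3.2 | serious bleed; severe bleeding; the bleeding event | delay or temporary stop; restart may be considered | none |
| 10.2.1 | significant bleeding event | temporary stop; may resume when judged safe | none for major bleeds |
| 10.2.2 | major bleeding event per 9.3.1 | should be stopped permanently | refers to 9.3.1 |

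Serious, severe and significant are not mapped to the three classes in 9.3.1, so 9.3.2 alone does not tell a site which bleeds bar a restart.

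**3. How does the protocol treat the other outcome that ends treatment?** For thrombotic events, 9.4 states that study drug must be permanently discontinued, which agrees with 10.2.2. The corresponding bleeding text in 9.3.2 permits restart.

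**4. How many children could be involved?** The documents give no expected major-bleed rate. Take 100 children (about 10 in Part A and 90 in Part B), independent, with an assumed rate of 1% to 5%:
- Expected major bleeds: 100 × 0.01 = 1, up to 100 × 0.05 = 5.
- Chance of none: 0.99^100 = 36.6% at 1%; 0.95^100 = 0.6% at 5%.

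These figures count major bleeds. The number restarted can only be equal or smaller, and the documents do not let it be estimated.

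**5. Which analyses would differ for such a child?**
- *First major bleed:* no change, because it precedes the restart decision.
- *Per-protocol Set:* the child is excluded if the restart is classed as a failure to discontinue permanently.
- *Compliance (SAP 3.4):* intended duration runs to Day 353 and is not cut at a major bleed. Assume a first dose on Day 1, a last dose on Day 100, and no death or thrombotic event. A permanent stop gives 100/353 = 28.3%. If drug is instead restarted and taken to Day 353, with d interruption days credited under 10.2.1, compliance is (353 − d)/(353 − d) = 100%. The first figure moves with the assumed day: 50/353 = 14.2% at Day 50 and 300/353 = 85.0% at Day 300. This is a descriptive summary and not a reason for the change.

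**The case against.** The strongest reply is that the sections can be read together. 10.2.2 is the dedicated stopping rule: it names major bleeding and points to its definition. 9.3.2 is acute-care guidance that says only what could or may be considered. A general permission need not cancel a specific rule, and it keeps its full meaning for bleeds that are serious but not major. An investigator who applies 10.2.2 breaches nothing in 9.3.2. This stands as a sensible reading, but the protocol does not state it, and the section cited for major bleeds does not lead the reader to 10.2.2.

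Oversight is a second reply. Serious bleeds are reported as serious adverse events within 24 hours, and the Independent Data Monitoring Committee regularly reviews bleeding events. A restart would probably be noticed. None of that text gives a restart rule, however, and detection may come after re-exposure.

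A reader might infer that 10.2.1 has the same conflict. The text does not support going that far. Significant and major bleeding appear in adjacent subsections titled temporary and permanent discontinuation, and are naturally read as tiers. Overlap is possible because significant is undefined, so a clarification there is useful, but it is secondary.

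**Conclusion.** The point holds as an unresolved inconsistency on the primary safety event. Read literally, 9.3.2 permits what 10.2.2 says should not happen. The conclusion rests on the wording of the two sections and on the footnotes that link 9.3.2 to major bleeds. The assumed bleed rates and the assumed Day 100 stop only illustrate scale.

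The effect is small in numbers: few or no children, no change to counts of first major bleeds, no hypothesis test, and per-protocol summaries that SAP section 5 makes optional. The change is worth making for patient safety and consistent site conduct.

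Three stronger readings are not supported:
- *That the protocol directs sites to restart after a major bleed.* It only allows restart to be considered.
- *That 10.2.2 is an absolute ban.* It says *should*.
- *That restart after any bleed is in conflict.* Non-major bleeds are not affected.

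**What to change.** In Protocol 9.3.2, end the last sentence with: *except after a major bleeding event (Section 9.3.1), for which study drug should be permanently discontinued per Section 10.2.2*. Keeping *should* matches the strength of 10.2.2.

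For clarity, add to the resumption sentence in 10.2.1 that it does not apply once a bleed meets the major bleeding definition, with a reference to 10.2.2. Keep the temporary hold for a significant bleed. Severity may be unclear at first, and SAP 1.6.3 gives sites up to 6 weeks just to send the adjudication package.

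The cost is two clauses in the protocol. The SAP, visits, data collection and sample size do not change, and restart after non-major bleeds stays at the investigator's judgment.
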